6.3. Protocol Deviations

Protocol deviations will be identified and documented in the clinical trial management system (CTMS) for inclusion in SDTM and ADaM. The protocol deviation data will be reviewed and assigned as important or non-important prior to database lock and unblinding.

Important protocol deviations are a subset of protocol deviations that may significantly impact the completeness, accuracy, and/or reliability of key study data or that may significantly affect a subject's rights, safety, or well-being. For example, important protocol deviations may include enrolling subjects in violation of key eligibility criteria or failing to collect data necessary to interpret primary endpoints, as this may compromise the scientific value of the trial.

Important protocol deviations will be summarized by treatment group, including Total Rodatristat ethyl and Overall, for each deviation category using the ITT population.

All protocol deviations and separately only important protocol deviations will be presented in a by-subject data listing.

6.4. General Medical History

All medical history conditions will be coded using the Medical Dictionary of Regulatory Activities (MedDRA). Medical history will be summarized by treatment group, including Total Rodatristat ethyl and Overall, by system organ class and preferred term, using the Safety population. Summaries will be ordered by descending order of the overall incidence of system organ class and preferred term within each system organ class.

General medical history data will be presented in by-subject data listings using the Safety population.

6.5. Non-Study Medications

6.5.1. PAH Medications

PAH medication currently being taken or taken within the past 3 months, as recorded on the PAH Medication eCRF, will be summarized with the number and percentage of subjects taking:

- Any Phosphodiesterase type-5 inhibitors (PDE-5i) and by type of PDE-5i (Sildenafil, Tadalafil, Vardenafil, or Other)

- Any Endothelin Receptor Antagonist (ERA) and by type of ERA (Ambrisentan, Bosentan, Macitentan, or Other)
- Any Soluble guanylate cyclase (sGC) and by type of sGC (Riociguat or Other)
- Any Prostacyclin and by type of Prostacyclin (Epoprostenol, Treprostinil, Iloprost, Selexipag, or Other)
- All possible combinations of the above

Concomitant PAH Medications, recorded on the Concomitant Medications eCRF, are defined as any medication coded to Anatomic Therapeutic Class (ATC) Level 4 ANTIHYPERTENSIVES FOR PULMONARY ARTERIAL HYPERTENSION or OTHER VASODILATORS USED IN CARDIAC DISEASES, or preferred names of EPOPROSTENOL or SELEXIPAG. Concomitant PAH Medications will be summarized and listed separately from other concomitant medications (see below, [Section 6.5.2](#)) by treatment group, including Total Rodatristat ethyl and Overall, for the Safety population.

6.5.2. Prior and Concomitant Medications

Prior medications are defined as medications that started before first study drug administration and either stopped before or continued after first study drug administration. Concomitant medications are defined as medications that are being taken while on study drug, within 28 days of last dose. Non-PAH concomitant medications are all other concomitant medications not included in the defined of PAH medications above ([Section 6.5.1](#)). Medications that are ongoing on the date of the first administration of study drug will be classified as both prior and concomitant. Any medication that cannot be confirmed as stopping before the start of study drug will be classified as both a prior and a concomitant medication. Imputation of partial dates is defined in [Appendix 1](#).

Prior and non-PAH concomitant medications will be summarized separately and the number and percentage of subjects in each treatment group who took at least one prior (non-PAH concomitant) medication as well as the number and percentage of subjects who took each type of medication will be summarized by Anatomic Therapeutic Class (ATC) Level 2, ATC Level 4, and preferred name for the Safety Analysis Set. If a subject has more than one occurrence of the same preferred name, then the preferred name will be counted only once for that subject. Similarly, if a subject has more than one preferred name within ATC Level 4 or ATC Level 4 within ATC Level 2, then the subject will be counted only once in that ATC Level 4 or ATC Level 2.

7. EFFICACY ANALYSES

Primary analyses of efficacy endpoints will be performed using the ITT population. Additional analyses may be repeated using the mITT, PP, and Treatment Completer populations, if the populations differ by >5% of total subjects in the ITT population.

All efficacy endpoints, recorded and derived, will be presented in by-subject data listings.

For applicable efficacy analyses, if the assumptions of the planned parametric analyses are violated and inhibit the interpretation of the results, appropriate data transformations or non-parametric analyses will be performed to support the interpretation of the treatment effect.

7.1. Statistical/Analytical Issues

7.1.1. Adjustments for Covariates

For comparison of treatment groups with respect to change and percent change from baseline, analysis of covariance (ANCOVA) and restricted maximum likelihood (REML) based mixed model repeated measures (MMRM) models will be used. The corresponding baseline value will be used as a covariate in the model.

7.1.2. Handling of Dropouts or Missing Data

The following methods will be implemented to address missing data for relevant primary, or secondary efficacy endpoints.

7.1.2.1. Missing at Random (MAR): Multiple Imputation

For the primary analysis of PVR, 6MWT, and NT-proBNP efficacy endpoints, subjects who miss an assessment for reasons other than death or other tolerability reasons, will be imputed using multiple imputation (MI) methodology based on the treatment group for time points at which no value is observed. An intercurrent event meeting will be held prior to database lock and unblinding with the medical monitor(s) and statistician(s) to review the missing efficacy assessments for each subject and determine if the missing data is MAR or missing not at random, (MNAR), i.e. informative missing.

MI will be performed under the assumption of MAR. Intermittent missing value(s) will also be replaced using MI. MI will impute 10 integer values using Markov Chain Monte Carlo (MCMC) methods assuming nonmonotone missing, a seed of 100201, 500 burn-in iterations, 100 iterations between imputations, and a non-informative prior. The imputation models based on treatment group will include randomization stratification factors, baseline WHO FC, baseline 6MWD, and baseline value of the endpoint and all previous values of the endpoint at each time point. Other baseline characteristics that may be explored will be documented in the CSR. It is anticipated that the imputation model will converge but should it not do so terms will be removed from the model to achieve convergence. The effects of any such model adjustment will be investigated.

Change from baseline to each post-baseline visit will be calculated based on observed and imputed data. Results from the analysis of each of the 10 imputed datasets will be combined using PROC MIANALYZE (Rubin's imputation rules, [Rubin 1987](#)).

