2.2. Double-Blind Phase Study Design

This study will compare the efficacy, safety, and tolerability of 2 dosing regimens of rodatristat ethyl to placebo in subjects with PAH over a 24 week treatment period. Investigational product (IP) will be administered on the background of stable PAH therapy.

Approximately ninety (90) evaluable subjects will be enrolled. Subjects will be randomized 1:1:1 to placebo, 300 mg BID, or 600 mg BID of rodatristat ethyl.

Eligible subjects will be stratified based on the number of background PAH therapies they are receiving (1 vs 2 vs 3) and selexipag use (Yes/No). The number of subjects who are on a prostanoid infusion will be capped at 50% of the total enrolled. The number of subjects who are receiving selexipag will be capped at 20% of the total enrolled.

The study will consist of a Screening Period (up to 28 days in duration), a Baseline Period (Day 1), a 24-week Treatment Period (Main Study), and for subjects that early terminate or do not enroll an Open Label Extension (OLE), and a 4 week Follow Up Period (approximately 4 weeks after the last dose), for a total study duration of 32 weeks.

Subjects who complete the Main Study will have the option to enroll into an OLE and continue to receive rodatristat ethyl (those randomized to placebo will be re-randomized 1:1 to receive rodatristat ethyl 300 mg BID or 600 mg BID) for 6.5 years, until the Investigator or subject chooses to stop the IP, any stopping criteria in the Main Study are met, IP becomes commercially available, or the Sponsor stops the study for lack of efficacy or a safety signal (whichever preceding criteria comes first). In no case will a subject be allowed to exceed 10 years of exposure unless the product is approved for a chronic indication.

All participating subjects will be required to be on a stable background therapy for PAH with mono, dual or triple combination therapy (which may include currently approved prostanoid therapies) at the time of Screening. All subjects will maintain their standard of care (SOC) regimen at entry for the duration of the study. Refer to Section 6.6.2 for more details.

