3. SAMPLE SIZE JUSTIFICATION

The sample size for this study was not based on a formal hypothesis testing. It is expected that 30 evaluable subjects per arm will provide sufficient data to assess safety and efficacy. Power calculations were conducted to examine the probability of detecting a difference among treatment groups for the percentage change of PVR from baseline.

A sample size of 90 subjects with 30 subjects to be randomized into 1 of the 3 treatment arms in a 1:1:1 randomization is planned. A sample size of 30 subjects per arm will provide at least 80% power at a significance level of 0.05 (2-sided hypothesis) to detect a treatment difference of 0.75 times of standard deviation (SD) in the percentage change from baseline of PVR from baseline between an active arm and the placebo arm. If the SD for PVR percent change is 24%, the study has 80% power to detect a difference of 18% between an active arm and the placebo arm.

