7.1.2.2. MNAR: Imputation for Deaths and Tolerability Reasons

For the primary analysis of PVR, 6MWT, and NT-proBNP efficacy endpoints, subjects who missed an assessment due to death, tolerability, or >10% change in parental prostainoid dose (including adding a new medication).will be imputed as the worst value in their planned treatment group at the specific visit.

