7.4.2. Time to Clinical Worsening (TTCW)

A clinical worsening event is defined using two definitions (a composite endpoint):

Protocol Definition

1. Death from any cause
2. Hospitalization for worsening PAH (any hospitalization for worsening PAH, lung or heart and lung transplantation, atrial septostomy, or initiation of parenteral prostanoid)
3. Disease progression, defined as a decrease of more than 15% from baseline in the 6MWD combined with WHO FC III or IV symptoms at 2 consecutive visits separated by at least 14 days. The time of disease progression is at the time of initial visit.

Additional Definition

1. Death from any cause
2. Hospitalization for worsening PAH (any hospitalization for worsening PAH, lung or heart and lung transplantation, atrial septostomy, or initiation of parenteral prostanoid therapy)

3. Disease progression defined as a decrease of more than 15% from Baseline in the 6-minute walk distance (6MWD) (2 consecutive visits separated by at least 14 days), combined with World Health Organization (WHO) Functional Class (FC) III or IV symptoms at 2 consecutive visits separated by at least 14 days. Also requires the absence of a clinical rationale (e.g., an intercurrent event that would be expected to worsen the walk and functional class independent of pulmonary hypertension progression).
4. Addition of parenteral prostanoid therapy or increase of greater than 10% of any prostanoid
5. Appearance of worsening signs and symptoms of right heart failure

TTCW will be adjudicated separately for each definition of clinical worsening. TTCW is defined as the first occurrence of any of the above events (separately for each definition).

The CEAC adjudicated CWEs include the date and reason will be incorporated into the clinical database. Adjudicated TTCW is defined as the number of days from randomization date to the date of the first adjudicated CWE. Subjects who do not have an adjudicated CWE during the 24 weeks of the main study will be censored at the first OLE dose date if enrolled into OLE or if not enrolled into OLE, the minimum of last dose of study drug + 30 days or date of last contact in the main study.

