11. CHANGES TO PROTOCOL PLANNED ANALYSES

- The exploratory objective “To evaluate the effect of rodatristat ethyl on the plasma concentration of selexipag and ACT333679” was reclassified as a PK/PD objective given it is assessing the drug concentrations.
- The Enrolled analysis set was relabeled to the “Screened” analysis set for clarity.
- The Safety analysis set was modified to include all subjects who received IP, regardless of randomization or not, to align with ICH E9 principles.
- The mITT analysis set was updated to specify at least one post-baseline PVR assessment (primary endpoint), instead of general efficacy assessment.
- The PP analysis set was updated to specify “who have completed treatment with $\geq 80\%$ treatment compliance” instead of general “complete Week 24”.

- The Treatment Completer analysis set was added.
- For primary endpoint analysis, missing data imputation was updated from LOCF to using multiple imputation for data MAR and worst observation for data NMAR.
- Analysis of WHO FC was updated from an ANCOVA model to ordinal logistic regression as it is a categorical endpoint.
- Analysis of 6MWT was updated from non parametric analysis of covariance within the framework of the extended Cochran Mantel-Haenszel test to aligned rank stratified Wilcoxon test with Hodges-Lehman estimates for consistency with drugs with similar indications.
- Physical examinations will be listed only.
- An additional definition of the TTCW endpoint was added.
- Additional exploratory endpoints added to specify all visits will be analyzed for secondary, additional, and exploratory endpoints where appropriate.
- Additional safety analyses were added to further characterize the risk profile.

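### PVR, 6MWD and NT-proBNP values missed because of PAH worsening without death or a prostanoid change are imputed as missing at random, so the primary PVR estimate does not respond to which arm worsened

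*SAP*

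**What the plan says.** The primary efficacy analyses use the ITT population (SAP 7), so a missing Week 24 value has to be filled in. SAP 7.1.2 does this by reason.

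- **Default (7.1.2.1).** "subjects who miss an assessment for reasons other than death or other tolerability reasons, will be imputed using multiple imputation (MI) methodology". The model is run by treatment group. It contains the stratification factors, baseline WHO FC, baseline 6MWD, the baseline value of the endpoint and its earlier values. A meeting before lock and unblinding reviews each subject's missing assessments and labels them MAR or MNAR.
- **Worst value (7.1.2.2).** "subjects who missed an assessment due to death, tolerability, or >10% change in parental prostainoid dose" (spelling as in the SAP) receive the worst value seen in their planned arm at that visit. Adding a new medication counts as a change.
- **Sensitivity (7.1.2.4).** Observed cases and the Treatment Completer population.
- **Clinical worsening (7.4.2, protocol definition).** Death; hospitalization for worsening PAH, spelled out as "any hospitalization for worsening PAH, lung or heart and lung transplantation, atrial septostomy, or initiation of parenteral prostanoid"; and a 6MWD fall of more than 15% with WHO FC III or IV, confirmed at a second visit. A committee adjudicates these events.
- **Summary of the change (11).** "multiple imputation for data MAR and worst observation for data NMAR".

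On measurement, the protocol schedule (1.3) has one RHC at screening and one at Week 24, with an early-termination RHC for patients who leave at or after Week 12. SAP 4.7.1, Table 4, counts any RHC from Day 2 to Day 197 as Week 24, provided it precedes the first OLE dose.

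**The concern.** The worst-value rule exists because some patients are missing for a reason that says their outcome was bad. A patient whose Week 24 RHC is missed after a lung transplant, a septostomy or an admission for worsening PAH is at least as clear a case as one who stopped for diarrhea. Yet the list in 7.1.2.2 names the second and not the first, although 7.4.2 treats the first as an endpoint event. The default rule then imputes that patient from arm-mates who stayed. At stake is whether the primary PVR comparison reflects a difference between arms in deterioration, in either direction.

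**Working it through.** **1. The plan's own figure.** SAP 3: "If the SD for PVR percent change is 24%, the study has 80% power to detect a difference of 18" per cent, with 30 per arm and two-sided alpha 0.05. The standard error is 24 x sqrt(2/30) = 6.20, and 18/6.20 = 2.90. Power by the normal approximation is Phi(2.905 - 1.960) = 82.8%; by the noncentral t with 58 df it is 81.5%. The stated figure of at least 80% is reproduced, so SD 24 and a difference of -18 are used below.

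**2. Reasons against rules.**

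| Reason the value is missing | In 7.4.2? | Rule as written |
|---|---|---|
| Death | yes | worst value |
| Tolerability | no | worst value |
| Parenteral prostanoid change >10% or new medication | initiation is | worst value in 7.1.2.2, but 7.1.2.1 does not exempt it |
| PAH hospitalization, transplantation, septostomy | yes | MI |
| Confirmed 6MWD/FC progression | yes | MI |
| Withdrawal for lack of efficacy | no | MI |

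**3. What MI knows about PVR.** There is no scheduled PVR between screening and Week 24, so the earlier values of the endpoint reduce to baseline. No post-baseline 6MWD, WHO FC, NT-proBNP or worsening status is in the model. A patient who deteriorated is imputed like an arm-mate with the same baseline.

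**4. Size.** The documents give no dropout rate by arm or reason, so the counts are assumptions. Let one arm of 30 lose m more worsening patients than the other, each truly w points worse. Truth here means the difference if every Week 24 PVR had been measured.

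- Excess on placebo: truth = -18 - m x w/30. With m = 2 and w = 30, -18 - 2 = -20.
- Excess on active: truth = -18 + m x w/30 = -16.
- Under MI each such patient is replaced by a typical arm-mate, so the expected estimate is -18 in both cases.

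The error is m x w/30 points. For m = 1, 2, 3 it is 0.5, 1.0, 1.5 with w = 15, and 1, 2, 3 with w = 30.

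**5. Simulation check.** 6,000 runs per scenario, 30 per arm, one active arm against placebo, w = 30, one same-arm random draw standing in for MI. Tolerability leavers are fixed at 3 active and 1 placebo.

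| Worsening leavers (active, placebo) | Truth | SAP rule | MI for all leavers |
|---|---|---|---|
| 1, 3 | about -20 | -15.0 | -18.0 |
| 2, 2 | about -18 | -14.7 | -18.1 |
| 3, 1 | about -16 | -15.0 | -17.9 |

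The truth moves by 4 points down the table; neither estimate follows it. The level near -15 under the SAP rule comes from the tolerability penalty: with the same tolerability leavers and no worsening leavers the result is -14.8.

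**6. What the worst value would do instead.** The expected maximum of 28 normal values is 2.01 SD, or 48.3 points above the arm mean. Two leavers move the arm mean by 2 x 48.3/30 = 3.2. The estimate becomes -21.2 against a truth of -20, or -14.8 against -16. It moves the right way and overshoots by 1.2, where MI misses by 2. The worst value is closer than MI only if w exceeds about half of 48.3, that is, about 24 points.

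**The case against.** Five points on the other side deserve weight.

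- **The meeting.** It can label a missed RHC after a transplant as MNAR, and Section 11 states the rule by mechanism. On that reading the patient gets the worst value. This narrows the gap without closing it: 7.1.2.1 states MI by reason, 7.1.2.2 has no worst-value rule for worsening, and the meeting has no written criteria.
- **Part of worsening is already covered.** Death and prostanoid change are triggers. This stands.
- **Worsening does not by itself create missing data.** Protocol 8.1 does not require withdrawal for progression, patients who stop IP are asked to keep attending, and an early-termination RHC counts as Week 24. With 6MWT and WHO FC scheduled at Weeks 4, 12 and 24, progression confirmed at scheduled visits before Week 24 is confirmed at Week 12, when that RHC applies. This stands, and it limits the exposed group mainly to patients who leave before Week 12 or have no early-termination RHC.
- **6MWD and NT-proBNP.** Their MI uses earlier values, so an observed decline informs the imputation. The argument in full applies to PVR.
- **Harm is not hidden overall.** Adjudicated worsening is analysed by arm in 7.4.2.

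A reader might also infer that the rule penalises mainly the active arms, because protocol 4.7 reports dose-dependent gastrointestinal events. The documents do not support that. They give no dropout by arm or reason, 4.7 describes those events as mild except for one moderate, and dose reduction and interruption are available. Protocol 6.6.1 does record one gastrointestinal discontinuation in the selexipag interaction study. The rule applies to placebo too: with one tolerability and one worsening leaver in each arm the simulation gives -18.0.

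**Conclusion.** The gap holds as a matter of text. Non-fatal PAH worsening without a prostanoid or medication change, and withdrawal for lack of efficacy, fall to same-arm MI. For the primary endpoint that MI cannot see the worsening. Neither planned sensitivity analysis helps, because both leave these patients' missing values out.

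The size is modest and its sign is unknown in advance: 2 points of the planned 18 for an excess of two leavers at 30 points each, and 0.5 to 3 points over the range shown. It understates the drug's effect if the excess is on placebo and overstates it if the excess is on active. Equal numbers give no bias. These figures rest on assumed counts and an assumed severity, and on a pairwise comparison without covariates or the Hochberg step.

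A reader might attribute a loss of 3 to 5 of the 18 points to this gap. That would be wrong. Two or three active tolerability leavers, with nobody missing on placebo, already give -14.8 and -13.2 (about 1.6 points each, 48/30). That loss is the tolerability penalty alone.

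**What to change.** Before database lock:

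- In SAP 7.1.2.2, extend the worst-value triggers to a value missed because of a CEAC-adjudicated clinical worsening event (protocol definition in 7.4.2), or because of withdrawal for lack of efficacy or disease progression, taken from the disposition reason. The adjudicated events do not capture lack-of-efficacy withdrawal, so the second source is needed; confirm that the disposition form offers those categories.
- In 7.1.2.1, limit MI to reasons other than those listed in 7.1.2.2. This also removes the mismatch over the prostanoid trigger.
- Have the intercurrent event meeting apply that list.
- Add one sensitivity analysis for these patients that shifts their MI values by a fixed amount, the same in every arm, from zero up to the worst value. This is needed because the worst value can overshoot. The SAP's reference list already includes a paper on pattern-mixture models in SAS.

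The cost is two sentences, an instruction to the meeting and one extra analysis. No new data are needed. The result becomes less favourable for whichever arm has more worsening leavers, which is the intent.

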7.1.6. Multiple Comparisons/Multiplicity

In order to control the Type 1 error rate for the primary efficacy endpoint, the comparisons between each active arm and the placebo arm will be tested using the Hochberg approach, where the two p-values (600 mg vs placebo and 300 mg vs placebo) will be ordered largest to smallest as $p(1) > p(2)$.

1. If $p(1) < 0.05$ then reject both null hypotheses.
2. If $p(1) > 0.05$, but $p(2) < 0.025$, then reject the null hypothesis associated with $p(2)$.

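### With only 10 imputations, a primary PVR result close to a Hochberg limit can be settled by Monte Carlo noise; raising the number is a free gain in precision

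*SAP*

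**What the plan says.** SAP 7.1.2.1 covers PVR, 6MWT and NT-proBNP values judged MAR. It states that "MI will impute 10 integer values using Markov Chain Monte Carlo (MCMC) methods", with "a seed of 100201, 500 burn-in iterations, 100 iterations between imputations, and a non-informative prior". It then says: "Results from the analysis of each of the 10 imputed datasets will be combined using PROC MIANALYZE".

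SAP 7 makes ITT the primary efficacy population, so a Week 24 PVR value that is missing and judged MAR has to be imputed. For the primary endpoint, SAP 7.1.6 (repeated in 7.2) says "the comparisons between each active arm and the placebo arm will be tested using the Hochberg approach". If the larger of the two p-values is below 0.05, both nulls are rejected. Otherwise the smaller is held to 0.025.

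Not every missing value goes through multiple imputation. Under SAP 7.1.2.2, values missing because of death, tolerability or a change of more than 10% in parenteral prostanoid dose receive the worst value in the arm. Under SAP Table 4, any catheterisation from Day 2 to Day 197 and before the first OLE dose counts as Week 24.

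The missing-data sensitivity analyses in SAP 7.1.2.4 are observed cases and Treatment Completers. The SAP sets no check on Monte Carlo error and no repeat run with other seeds.

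**The concern.** Ten imputations look ample on the usual efficiency measure. With a fraction of missing information (FMI) of 0.11, relative efficiency is 1/(1 + 0.11/10) = 0.989, a loss of about 1%. That measures the variance of the estimate. It does not show how far the pooled p-value moves when the same data are imputed again with another seed, and that is what counts when the p-value is compared with a sharp limit.

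Fixing the seed makes the analysis repeatable but leaves the Monte Carlo error where it was. If the p-value that very many imputations would give lies near 0.025 (or, for the larger of the two, near 0.05), the primary conclusion for a dose can turn on an arbitrary number. PVR is especially exposed because SAP 7.4.1 schedules it only at Screening and Week 24, so there is normally no intermediate PVR to inform an imputed value.

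**Working it through.** **Inputs from the documents.** 30 per arm, 1:1:1, difference 18%, SD 24%, two-sided 0.05 (SAP 3); 10 imputations and Rubin pooling (SAP 7.1.2.1); ANCOVA on percent change (SAP 7.2); Hochberg limits 0.05 and 0.025 (SAP 7.1.6).

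**Assumptions.** The MAR-missing share of Week 24 PVR is not stated, so 3%, 10% and 20% per arm are shown (1, 3 and 6 of 30). The correlation between baseline covariate and outcome is set at 0.3. Imputation is by arm, using a Bayesian normal regression.

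**Step 1: the plan's own figure.** SAP 3 states: "A sample size of 30 subjects per arm will provide at least 80% power". By the normal approximation, 18/(24 × √(2/30)) = 2.905, and 2.905 − 1.960 = 0.945, which gives 82.8%. The t-test gives 81.5%. The stated power reproduces.

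**Step 2: analytic size of the noise.** Across seeds, the SD of the pooled z is about √(FMI/m). At 10% missing, FMI is about 0.11. A two-sided p of 0.025 corresponds to z = 2.24.

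- m = 10: √(0.11/10) = 0.105. So z = 2.24 ± 1.96 × 0.105 = 2.24 ± 0.21, and p runs from about 0.014 to 0.042.
- m = 100: √(0.11/100) = 0.033. So z = 2.24 ± 0.065, and p runs from about 0.021 to 0.030.

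**Step 3: simulation near the limit.** The effect was tuned so that p with very many imputations was about 0.025. The same data were then re-imputed with 200 to 400 seeds. Central 95% of pooled p:

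| MAR-missing per arm | FMI | m = 10 | m = 100 | m = 200 |
|---|---|---|---|---|
| 1 of 30 (3%) | 0.046 | 0.018–0.037 | 0.023–0.028 | 0.023–0.028 |
| 3 of 30 (10%) | 0.111 | 0.015–0.043 | 0.020–0.030 | 0.022–0.029 |
| 6 of 30 (20%) | 0.208 | 0.010–0.070 | 0.020–0.036 | 0.021–0.032 |

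At 10% missing, the SD of p across seeds is 0.008 with 10 imputations and 0.003 with 100. The simulation agrees with Step 2.

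**Step 4: how often it matters over all trials.** The full Hochberg rule was simulated with 4,000 trials per cell, comparing 10 imputations with 400. At the planned 18% difference, any Hochberg decision differed in 2.7%, 5.4% and 10.3% of trials at 3%, 10% and 20% missing. With no true effect it differed in 0.8% to 2.2%.

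**Step 5: operating characteristics.**

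| | m = 10 | m = 400 |
|---|---|---|
| At least one false rejection, 10% missing | 4.5% | 4.4% |
| At least one false rejection, 20% missing | 5.2% | 4.8% |
| Power for at least one dose, 10% missing | 85.2% | 85.8% |

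**The case against.** The best defence is that little is at stake. Rubin's rules already carry the extra variance from a finite number of imputations, so type I error and power barely move (Step 5). The seed was set in advance and cannot be picked after the results are seen. The share of values imputed as MAR may be small: worst-value cases add no seed noise, and the protocol asks for an RHC at early termination at or after Week 12 (Section 1.3 footnote 14; Section 8.2.1), which Table 4 turns into a Week 24 value. Observed-case and completer analyses, which contain no imputation noise, are planned alongside. SAP 3 also says the sample size did not rest on formal hypothesis testing.

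Most of this stands, and it limits the size of the point. It does not remove it. SAP 1 states that the SAP supersedes the protocol's statistical section, and SAP 7.1.6 and 7.2 set a formal test with error control. Having chosen a sharp rule, the plan should compute its p-value accurately enough to apply it. The sensitivity analyses answer a different question and would not reveal seed dependence.

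A reader might infer that some four in ten trials would be decided by the seed. The documents do not support that. A figure of 39% of seeds crossing 0.025 (17% with 100 imputations) arises at 10% missing, but only for data sets whose many-imputation p-value already lies between 0.020 and 0.025. At the planned effect, one comparison falls in that band in about 3% of trials. The unconditional figures in Step 4 are the ones to use.

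**Conclusion.** The point holds as a precision weakness in the primary PVR analysis. With 10 imputations, a PVR p-value near a Hochberg limit is not determined finely enough by the data and model alone. At the planned effect this changes a decision in about 3%, 5% and 10% of trials at 3%, 10% and 20% MAR-missing, and in none if no PVR value is imputed as MAR. These figures rest on the assumed missing share, the assumed correlation of 0.3 and a simplified imputation model.

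Three stronger readings should be set aside:

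- **The test is invalid or type I error is inflated.** It is not; false rejections are essentially the same with 10 and 400 imputations.
- **0.025 is always the operative limit.** It applies only when the larger p-value exceeds 0.05. If both are below 0.05, both doses are rejected and the relevant limit is 0.05.
- **The same size of problem applies to 6MWD and NT-proBNP.** They share the imputation setting, but the Hochberg step is confined to the primary endpoint. They are analysed by an aligned rank test (SAP 7.3.2) and an MMRM (SAP 7.3.3), and have Week 4 and Week 12 values to inform imputation. No size of effect was calculated for them and none is claimed.

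**What to change.** In SAP 7.1.2.1, replace 10 imputations with at least 100, or more if computing time allows, and keep the pre-specified seed. Change the matching count in the pooling sentence. Add a requirement to report the Monte Carlo error of the pooled PVR p-values, because a larger number narrows the uncertain band without closing it. The same setting can be used for 6MWD and NT-proBNP for consistency.

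The cost is a small edit to one section and a few minutes of computing. No data collection, sample size or test procedure changes.
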